3.0 Eligibility

1. Histological confirmation of non-small cell lung cancer (squamous cell carcinoma, adenocarcinoma, large cell carcinoma, bronchoalveolar cell carcinoma, or non-small cell carcinoma NOS) by either biopsy or cytology.
2. Clinical AJCC stage IIA (T1N1M0), IIB (T2,N1M0, T3,N0,M0) or IIIA (T1-3, N1-2,M0)/selected IIIB. In all cases, patients may be included at the discretion of the treating radiation oncologist if it will be likely the disease can be encompassed by the stereotactic boost.

3. Patients with non-bulky (<2.0-3.0 cm) hilar or mediastinal lymphadenopathy determined by pre-treatment CT scan, PET or mediastinoscopy
4. Must have completed a standard course of chemoradiation in accordance with NCCN Guidelines
5. One month following definitive chemoradiation, CT or PET-CT revealing limited volume residual disease within the site of primary tumour mass (post- chemo/RT mass </= 7.0 cm). Patients with a CR and no obvious target are not eligible.
6. must be able to fit into the Civco stereotactic immobilization device.
7. Patients must be \geq 18 years of age.
8. The patient's ECOG performance status must be 0-2.
9. Women of childbearing potential and male participants must use an effective contraceptive method.
10. Patients must sign a study-specific consent form.

3.1 Exclusion Criteria

1. Any other active cancer.
2. No prior malignancy is allowed except for the following: adequately treated basal cell or squamous cell skin cancer, in situ cervical cancer or other cancer from which the patient has been disease-free for 5 years.
3. Patients with other systemic illness, or have not recovered adequately from their primary treatment or who have evidence of progression of their lung cancer prior to therapy that, in the investigators opinions, would preclude their inclusion
4. Plans for the patient to receive other concomitant antineoplastic therapy while on this protocol, except at disease progression. Patients may be allowed to use bisphosphonates for hypercalcemia.

5. Pregnant or lactating women

4.0 PRETREATMENT EVALUATIONS

(All lab tests and radiographic studies should be done at approximately 3 weeks post chemoradiation)

- 4.1** Complete history, physical examination, and evaluation of Zubrod Performance Status.
- 4.2** Pathological (*biopsy*) or cytologically proven non-small cell lung cancer.
- 4.3** Postchemoradiation CT with contrast or PET/CT (preferred) of chest and upper abdomen to include the liver and adrenals; baseline brain MRI or CT scan.
- 4.4** Bone scan, only if the patient has bone pain and/or and elevated alkaline phosphatase.
- 4.5** Pulmonary function tests - including DLCO and FEV1
- 4.6** CBC; serum chemistry tests to include alkaline phosphatase, glucose, creatinine, electrolytes, AST (*SGOT*), and total bilirubin,

5.0 Treatment Plan

5.1 Radiation Therapy - Primary chemoradiation

All initial chemoradiation must be planned and delivered with CT-based 3-d planning. Like any radiation oncology boost therapy, as part of the pre-SBRT boost therapy assessment, complete and detailed dosimetry from the primary chemoradiation must be made available. The purpose is to ensure dose constraints on normal tissues are respected. The recommended radiation plan format is elucidated below and follows standard radiation oncology practice. Detailed chemoradiation plan must be reviewed during planning of the SBRT boost.

Volume and ICRU Reference Point Definitions

The definitions of volumes will be in accordance with the 1993 ICRU Report #50:45 Prescribing, Recording and Reporting Photon Beam Therapy.

5.1.1 Gross Tumor Volume (GTV) is defined by the physician as all known gross disease as defined by the planning CT and clinical information. Gross tumor includes the primary tumor (*GTV-P*) and abnormally enlarged regional lymph nodes > 1.0 cm (*short axis*

measurement) (GTV-N).^{46,47,48,49} These volume(s) may be disjointed. Note ICRU Report #50 also defines a clinical target volume (*CTV*) which may include the area of subclinical involvement around the GTV.

5.1.2 Planning Target Volume (PTV) will provide margin around the GTV to compensate for variabilities in daily treatment setup and internal CTV motion due to breathing or motion during treatment. The PTV for which dose escalation will be occurring must include the entire GTV plus a minimum 3D margin of 10mm. More margin may be necessary if the tumor movement is increased because of physiologic movement which should be checked, in most cases by fluoroscopy.

5.1.3 The *ICRU Reference Point* is to be located in the central part of the PTV. Typically this point should be located on the beam axis or at the intersection of the beam axes (*isocenter*).

5.2 3D Planning

5.2.1 Planning Volume (PTV) - The PTV is to be treated with any combination of coplanar or noncoplanar 3-dimensional conformal fields shaped to deliver the specified dose while restricting the dose to the normal tissues. Field arrangements will be determined by 3D planning to produce the optimal conformal plan in accordance with volume definitions. The treatment plan used for each patient will be based on an analysis of the volumetric dose including DVH analyses of the PTV and critical normal structures.

5.2.2 Dose Specification : Radiation therapy: Patients will be have CT planning designed to encompass all known disease. While mediastinal coverage is recommended, fields will be at discretion of the treating physician in accordance with standard therapy. Recommended plans will give patients initial fields using AP:PA plans to approximately 3960cGy, followed by off cord boost to a final dose of 5940 cGy or higher. Alternative plans respecting dose limiting organ tolerances would be acceptable. All patients will be treated at 180-200 cGy/day on minimum 6 mV linear accelerators or higher energies. All attempts are to be made to cover contoured GTV's by minimum a 95% of prescribed dose.

5.2.3 All patients will have 3-d planning with attention to dose limiting organs. Complete dose volume histograms must be provided and include (at a minimum) spinal cord, esophagus, brachial plexus as appropriate, combined lung volumes (to estimate V₂₀), heart, gross tumour volume (may have separate GTV's for primary tumour and nodes), planning target volume (GTV+ 1.0-2.0 cm at the discretion of the treating physician)

[figure not shown]
5.3 Normal Tissue Volume and Tolerances

5.3.1 The tolerance of the lungs is related to the volume of the organ(s) irradiated. Data from the Washington University (12) reported that high-grade acute pneumonitis did not occur when the V₂₀ was </= approximately 30%. The incidence and the grade or severity of pneumonitis was clearly related to the V₂₀. Total lung volume is defined as the lung volume of both lungs minus the PTV. In the Washington University data, maximum dose (*with conventional fractionation*) was not related to acute pneumonitis. For this protocol all eligible patients the goal is to attempt to have the V₂₀ < 30% although higher percentages are acceptable at the discretion of the treating physician. It is expected that the dose to the lungs will be the primary dose-limiting structure. Every effort to keep the total lung dose to a minimum should be performed. Since most lung tumors are localized to one lung, efforts to keep the contralateral lung at a minimum should also be performed. The patient's overall lung function is evaluated by the FEV1 and DLCO should also be evaluated in determining an individual's lung function reserve and thus the ability to radiate.

5.3.2 When planning the beam arrangement to the PTV, the heart, esophagus, and spinal cord should be out of the field to the extent possible. The dose per fraction to the lungs, heart, esophagus, and spinal cord should be maintained at 2 Gy or less per fraction to the extent possible. If tolerance dose to any of the normal organs is exceeded, alternate beam arrangements should be used.

5.3.3 Tumors will be classified as being either medial or peripheral based on the planning CT scan obtained for treatment planning. This definition will be based on the same designation for RTOG 0813: including any tumor within the zone of the proximal bronchial tree", which is a 2 cm radius around the main tracheo-bronchial tree: trachea;

left and right main stem bronchi; right upper, middle, and lower lobe bronchus; and left upper, lingular, and lower lobe bronchus. This can be represented in the figure below:

5.3.4. General considerations for organ tolerances

ORGAN	VOLUME	TOLERANCE DOSE TD _{5/5}	END POINT
Lung	Ipsilateral whole lung Contralateral lung (only if necessary)	25 Gy 20 Gy	Clinical Pneumonitis
Esophagus	1/3 2/3 3/3	65 Gy 58 Gy 55 Gy	Clinical Stricture and Perforation
Brachial Plexus	point dose	60 Gy	Clinically Manifested Nerve Damage
Spinal Cord	5 cm 10 cm 20 cm	50 Gy 50 Gy 47 Gy	Myelitis Myelitis Myelitis
Heart	1/3 2/3 3/3	66 Gy 50 Gy 40 Gy	Clinical Pericarditis Clinical Pericarditis Clinical Pericarditis
Liver	1/2 2/2	35 Gy 30 Gy	Clinical Hepatitis Clinical Hepatitis

6.0 Stereotactic Dose Specifications

6.1.1 Stereotactic Targeting and Treatment

Targeting, planning, and directing of therapy will be accomplished using beams of radiation along any trajectory in 3-D space focusing on the target, which will be of known 3-D coordinates. A fixed 3-D coordinate system defined by fiducials will be

used. This coordinate system will be directly related to the radiation producing device in a reproducible and secure fashion and will be used to define the position of the target(s) within the patient. Each treatment is designed to direct the radiation toward an isocentre according to known 3-D coordinates determined during treatment planning. In this study, the fiducials will be radio-opaque markers placed at known locations within a frame adjacent to the patient.

6.1.2 Patient Positioning

The patient's position must be accurately reproducible from treatment to treatment. Uncomfortable positions should be avoided to prevent movement during treatment. The immobilization system used in this trial will be a stereotactic frame that surrounds the patient on three sides and references the stereotactic coordinate system. Within this frame, the patient will be positioned on large, rigid pillows that conform to patients' external contours.

6.1.3 Inhibition of Effects of Internal Organ Motion

Reliable abdominal compression (the effectiveness of which will be checked via fluoroscopy) will be used to minimize the effect of internal organ motion (i.e. breathing, etc.) on target positioning and reproducibility. This will be performed such that the GTV does not deviate beyond the confines of the PTV with any significant probability (i.e. <5%).

6.1.4 Localization

Immediately before each treatment, isocentre port localization films (anterior/posterior and lateral) will be obtained on the treatment unit to ensure proper alignment of the isocentre.

6.2 Treatment Planning/Target Volumes

6.2.1 Image Acquisition

Treatment planning will utilize Computed Tomography (CT). The planning CT will be obtained with the patient in the body frame to allow simultaneous view of the patient's anatomy and the fiducial system. To better delineate between tumor and adjacent vessels or atelectasis, IV contrast will be used during planning CT acquisition unless

contraindicated (i.e. the patient has poor renal function or allergy to contrast media). 3.0mm thick axial slices will be obtained with the gantry at 0 degrees. An appropriately trained physician will outline the target lesion and designate it as the Gross Tumor Volume (GTV). This will be accomplished using pulmonary windows or soft tissue windows with contrast. Only abnormal density on CT consistent with gross tumor will be included in the GTV, with no enlargement of the target for “margin” to account for presumed microscopic extension (i.e. GTV and Clinical Target Volume (CTV) are to be identical). The Planning Treatment Volume (PTV) will consist of the GTV with an additional 0.5 cm in the axial plane and 1.0 cm in the longitudinal (cranio-caudal) plane.

6.2.2 Dosimetry

Each case will have three-dimensional non-coplanar (and occasionally coplanar) beam arrangements custom designed to deliver highly conformal prescription dose distributions per the UK institutional standard. 7 or more beams (minimum 7 beams) with roughly equal weighting will be used, with more beams being used for larger lesions. The isocentre will be defined as the common point of gantry and couch rotation for the treatment unit. The isocentre in stereotactic coordinates will be determined from system fiducials and translated to the treatment record. The field aperture size and shape will correspond nearly identically to the projection of the PTV along a beam’s eye view, except when observing the minimum field dimension of 3.5 cm in the treatment of small lesions. Prescription lines covering the PTV will generally be the 80% line. Hotspots will be manipulated to occur within the target and not within adjacent normal tissue.

The prescription dose of **with inhomogeneity correction** to the 80% isodose line times 2 fractions will be delivered to the margin of the PTV covering a minimum of 95% of the PTV. For purposes of dose planning and calculation of monitor units for actual treatment, all tissues within the body, including lung, will be assumed to have unit (water) density (no correction for tissue heterogeneity).

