2.0 Objectives

Primary

1. to determine the toxicity of the SBRT boost dose by estimating the proportion of subjects enrolled who develop pneumonitis

Secondary

1. to determine response rates of the residual primary tumor following SBRT boost

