6.2.3 Dose and Fractionation

The dose and fractionation scheme utilized will be based on the location of the patient’s residual disease. For patients with:

Peripheral Tumors: Treatment will consist of 2 fractions of radiation, with a minimum of 40 hours separating each fraction. Two fractions of 10 Gy with inhomogeneity

correction will be delivered to the prescription line at the edge of the PTV for a total of 20 Gy. This will yield a total BED of 110 Gy.

Medial Tumors: Treatment will consist of 3 fractions of radiation, with a minimum of 40 hours separating each fraction. Three fractions of 6.5 Gy with inhomogeneity correction will be delivered to the prescription line at the edge of the PTV for a total of 19.5 Gy. This will yield a total BED 102.2 Gy.

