6.3.3 Critical Organ Dose-Volume Limits

All critical organ dose volume limits must take into account the initial dose delivered during chemoradiation. All initial chemoradiation must have been planned with 3-d CT planning. Typically, chemoradiation is given to 59.4-66 Gy and organs such as spinal cord and esophagus reach significant doses of radiation. Commonly the tolerance of spinal cord is considered to be 50 Gy (180-200cGy/fraction). Prior to boost stereotactic radiotherapy, all previous radiation plans must be reviewed with dose-volume histogram analysis to determine critical organ doses. In considering the stereotactic plan, if a minimum of 7 beams are used, each is contributing only approximately 140cgy of the

total prescribed dose. If any beam traverses a critical organ, the dose delivered will be considered and a maximum point dose to any organ considered.

Table 5.3.3 lists maximum dose limits to a point or volume within several critical organs to be considered when standard (180-200cGy) fractionation is given. Size of fraction delivered to each organ during stereotactic treatments must be considered, since not all beams will either enter or exit through a structure. Every attempt to keep entrance and exit doses of each fraction of SBRT traversing a critical organ to as close to a **maximum** of 200 cGy as possible to help estimate critical structure doses. All critical organs will be contoured and doses calculated in a standard fashion. Composite plans incorporating the initial radiotherapy and the stereotactic boost must be created to accurately assess tolerances.

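### Sections 6.2.2 and 6.2.3 put the SBRT boost on two incompatible dose-calculation bases, so the physical boost dose is not uniquely defined

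*Combined protocol and SAP*

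**What the plan says.** Section 6.2.2 (Dosimetry) has two adjacent sentences on how the boost dose is calculated.

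- The first puts the prescription on the inhomogeneity-corrected basis and specifies it as "to the 80% isodose line times 2 fractions will be delivered to the margin of the PTV covering a minimum of 95% of the PTV".
- The second opens "For purposes of dose planning and calculation of monitor units for actual treatment" and continues that "all tissues within the body, including lung, will be assumed to have unit (water) density (no correction for tissue heterogeneity".

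Section 6.2.3 (Dose and Fractionation) returns to the corrected basis for both tumor locations. For peripheral tumors the wording is "Two fractions of 10 Gy with inhomogeneity", completed by the same reference to correction, with 20 Gy in total and a stated cumulative BED of 110 Gy. For medial tumors it says "Three fractions of 6.5 Gy with inhomogeneity correction will be delivered to the prescription line at the edge of the PTV", 19.5 Gy in total, with a stated cumulative BED of 102.2 Gy.

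Two other parts of the protocol depend on this dose. The primary objective in section 2.0 is "to determine the toxicity of the SBRT boost dose by estimating the proportion of subjects enrolled who develop pneumonitis". Section 6.3.3 requires that "Composite plans incorporating the initial radiotherapy and the stereotactic boost must be created to accurately assess tolerances".

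**The concern.** The uncorrected sentence in 6.2.2 is the only one in the protocol that says how monitor units are computed. A physicist who follows it plans as if lung were water. Where beams cross lung, the monitor units obtained that way will not in general deliver the corrected dose that 6.2.3 says will be delivered.

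Three things rest on the dose actually given:

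- the exposure whose toxicity is the primary objective;
- the BEDs of 110 and 102.2 Gy, which carry the rationale for the boost;
- the composite organ-dose checks, in patients whose organs have already received substantial dose.

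Even if every patient was planned the same way, a reader cannot tell from the protocol which dose the pneumonitis proportion describes, and another centre could not reproduce it.

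**Working it through.** **Step 1: compare the instructions.**

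| Place | What it governs | Basis |
|---|---|---|
| 6.2.2, prescription sentence | prescribed dose | corrected |
| 6.2.2, next sentence | planning and monitor units for actual treatment | uncorrected |
| 6.2.3, peripheral | delivered dose, 2 x 10 Gy | corrected |
| 6.2.3, medial | delivered dose, 3 x 6.5 Gy | corrected |

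This cannot be read as one basis for reporting and another for delivery. The uncorrected sentence names actual treatment, and 6.2.3 speaks of the dose to be delivered. The reference in 6.2.2 to the institutional standard concerns beam arrangements and conformal dose distributions; it names no calculation basis. No other section says which basis governs or gives a conversion.

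**Step 2: reproduce the protocol's BEDs.** The formula in section 1.2 is BED = nd(1 + d/10), taking alpha/beta as 10.

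- Base, 59.4 Gy in 1.8 Gy fractions (section 1.3): 33 x 1.8 x 1.18 = 70.09.
- Peripheral boost: 2 x 10 x 2 = 40.00. Total 110.09 (stated 110).
- Medial boost: 3 x 6.5 x 1.65 = 32.175. Total 102.27, or 102.175 with the base rounded to 70 (stated 102.2).

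The arithmetic is right, but it holds only if the nominal fraction dose is the dose delivered.

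**Step 3: sensitivity to the delivered dose.** The documents give no size or sign for the corrected/uncorrected difference, so these ratios of delivered to nominal dose are assumptions. The base is 70.09.

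| Delivered / nominal | Peripheral total BED | Medial total BED |
|---|---|---|
| 0.80 | 98.9 | 93.8 |
| 0.90 | 104.3 | 97.9 |
| 0.95 | 107.1 | 100.1 |
| 1.00 | 110.1 | 102.3 |
| 1.05 | 113.1 | 104.5 |
| 1.10 | 116.3 | 106.9 |
| 1.20 | 122.9 | 111.7 |

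**Step 4: shortfall that reaches the 100 Gy BED target of section 1.3.** Let s be delivered dose divided by nominal dose, and B the base BED.

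- Medial: 19.5s + 12.675s² = 100 − B.
- Peripheral: 20s + 20s² = 100 − B.

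Section 5.2.2 allows 180-200 cGy per day, and section 6.3.3 says "Typically, chemoradiation is given to 59.4-66 Gy and organs such as spinal cord and esophagus reach significant doses of radiation". Three base schedules within those limits give:

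| Base schedule | B | Medial s (shortfall) | Peripheral s (shortfall) |
|---|---|---|---|
| 33 x 1.8 = 59.4 Gy | 70.09 | 0.949 (5.1%) | 0.821 (17.9%) |
| 30 x 2 = 60 Gy | 72.00 | 0.904 (9.6%) | 0.785 (21.5%) |
| 33 x 2 = 66 Gy | 79.20 | 0.725 (27.5%) | 0.636 (36.4%) |

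These are tolerances for tumor BED at the PTV edge. They do not estimate the dose discrepancy and say nothing about lung dose or pneumonitis.

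**Related point.** The prescription sentence in 6.2.2 specifies two fractions without limiting this to peripheral tumors. The schema and 6.2.3 give three for medial tumors.

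**The case against.** The best defence is that this is an unfinished edit and the dose itself was never in doubt. Three statements say corrected and one says uncorrected, and 6.2.3 is the section that sets the doses. The corrected wording in 6.2.2 sits in a broken sentence, which would fit a later insertion that left older text behind. The trial appears to be a single-institution pilot, and one department would probably use one basis throughout. In that case the pneumonitis proportion is still a valid estimate for the treatment as given, and stating the basis in the report would cure the rest. The BED figures are tolerances against a tumor-control target, whereas the primary endpoint is pneumonitis. The fraction count in 6.2.2 is settled by the section that follows it.

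Much of this stands. The documents show no mixed planning, the BED figures cannot measure the effect on the primary endpoint, and the fraction-count point is minor. The editing history, however, is inference. A count of statements does not settle which one governs, because the outlying sentence is the only instruction on monitor units. Consistent practice would protect the estimate but would not tell a reader of the protocol what dose it refers to.

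**Conclusion.** The contradiction is real and must be fixed. The instruction for calculating the experimental treatment conflicts with the dose the protocol says will be delivered, and the primary objective is the toxicity of that dose.

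The size and direction of the resulting dose difference cannot be derived from the documents, and no effect on pneumonitis is claimed. Under the protocol's own BED model, the margin to the 100 Gy target is thin only for medial tumors at or near the minimum base dose; elsewhere it is wider. The stated BEDs are arithmetically correct for the nominal doses, and the sample-size and stopping-rule calculations do not depend on this point. The conclusion rests on the text of 6.2.2 and 6.2.3 and on beams crossing lung. It takes no view on which basis is right.

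**What to change.** - Reconcile 6.2.2 with 6.2.3 so that one stated dose-calculation basis applies to both the prescription and the monitor units. The choice belongs to the sponsor's radiation and physics team.
- Have 6.2.2 refer to 6.2.3 for the number of fractions.
- For any patients already treated, record from the planning files which basis was used, and report the pneumonitis rate against that basis.
- Recompute plans on a common basis only if the records show that more than one was used.

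The cost is a short amendment and a check of the planning records. Recalculation is needed only if the check finds mixed bases.
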